### **Study Objective & Study Design**

This mixed-methods study comprising a 3-arm pilot RCT and a qualitative study aims to investigate the preliminary effects and feasibility of a home-based combined activity and cognitive intervention for ICU survivors (COMBAT-ICU). Adopting a 3-arm design with COMBAT-ICU, exercise and attention placebo study arms will enable us to evaluate the added effects, if any, of the novel combined intervention compared with the standard

exercise-only rehabilitation strategy and attention placebo. Data triangulation from quantitative and qualitative aspects can facilitate result interpretation. The study's objectives are:

1. To evaluate the preliminary effects of the COMBAT-ICU intervention for ICU survivors on PICS, physical, mental and cognitive outcomes, HRQoL, unplanned re-hospitalisation rate, and mortality.
2. To explore the feasibility and acceptability of the COMBAT-ICU intervention and ICU survivors' intervention engagement experience.

The hypothesis of the first objective is that upon completion of the COMBAT-ICU intervention, ICU survivors will have reduced PICS, improved physical function, mental health, cognition and HRQoL, and reduced unplanned readmissions and mortality compared with the exercise and attention placebo groups at post-intervention and 3 months thereafter. While the hypothesis of the second objective is that the COMBAT-ICU intervention is feasible and acceptable for ICU survivors.

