## **Sample Size**

For the sample size of the pilot RCT, as no previous study has tested the effects of a similar intervention, we conservatively assume a small effect size (i.e. between 0.1 and <0.3) on the primary outcome (i.e. PICS). According to the method proposed by Whitehead et al., a sample size of 20 per study group would give the main trial 80% power at a 5% level of significance to detect between-group changes in the outcome at the post-intervention time points. The total sample size is therefore 60. All participants in the COMBAT-ICU group will be invited to participate in the subsequent qualitative study.

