### **Primary and Secondary Outcomes**

The following validated performance-based and patient-reported measures will be used for outcome evaluation at baseline (T0), immediate post-intervention (T1) and 3 months post-intervention (T2):

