#### *Primary outcome*

**Patient-reported PICS:** The 18-item Post-Intensive Care Syndrome Questionnaire (PICSQ) will be used to measure the extent of PICS. The PICSQ consists of 3 subscales, physical, cognitive and mental, and is rated on a 4-point Likert scale ranging from 0 to 3. It has good internal consistency (Cronbach's alpha = 0.93). Its criterion validity is evidenced by its strong correlation with frailty and HRQoL measures, and factor analysis confirmed its construct validity.

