### **Methods of Data Analysis**

Descriptive statistics will be used to summarize the recruitment, attendance and retention rates, the cost of implementation, and participant satisfaction. The RCT data will be analyzed according to the intention-to-treat principle. The study groups' baseline characteristics will be compared using the chi-square test, Kruskal-Wallis test or one-way analysis of variance (ANOVA) where appropriate. In line with the findings of a recent meta-analysis, the following variables will be treated as potentially confounding variables: age, sex, previous mental health problems, disease severity (APACHE II score), and negative ICU experience (measured by the Intensive Care Experience Questionnaire). Variables with p-values  $\leq 0.10$  for between-group differences at baseline will be statistically adjusted in the analysis. Generalized estimating equation modelling will be performed to determine the effects of the COMBAT-ICU intervention by comparing the intervention group with the exercise and attention placebo groups across the study time-points. All statistical analyses will be performed using IBM SPSS 28.0. All statistical tests will be two-sided, and the significance level will be set at 0.05.

For the qualitative data, the audio-recorded interviews will be transcribed verbatim. After checking the accuracy of the transcriptions, content analysis will be performed to code the data on participants' acceptability and perceived effects of the intervention. The technique of joint displays using an informational matrix will be used to integrate quantitative and qualitative data in order to seek for convergence of results. The trustworthiness of the qualitative analysis will be enhanced by audio-recording the interviews, conducting an audit trail, and involving two project team members in coding the data independently and developing the categories, subcategories and themes.

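### GEE with tests at 0.05 on 20 participants per arm carries no small-sample provision; in its ordinary large-sample forms a single contrast has a type I error of about 5.5% to 6.4%

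*Protocol*

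**What the plan says.** Under Methods of Data Analysis the protocol states that "Generalized estimating equation modelling will be performed to determine the effects of the COMBAT-ICU intervention". The model is to contrast COMBAT-ICU with each of the other two arms over the visits. The level is set in the same paragraph: "All statistical tests will be two-sided, and the significance level will be set at 0.05". It also names the software: "All statistical analyses will be performed using IBM SPSS 28.0".

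The Sample Size section gives "a sample size of 20 per study group", 60 in total. Outcomes are measured at three visits: baseline, end of intervention and three months later. The primary outcome, the PICSQ, has 18 items each scored 0 to 3, so it runs from 0 to 54 if the items are summed. Most secondary outcomes are scores, times or distances; readmission and mortality are the main exceptions.

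The protocol gives no working correlation, variance estimator, small-sample correction, or t or F reference. It does not say that an uncorrected sandwich variance will be used. Under Study Objective & Study Design it says that the study "aims to investigate the preliminary effects and feasibility" of the intervention.

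**The concern.** GEE inference is justified by a large number of independent units. Here each two-arm contrast rests on 40 people. With so few, two things push the test away from its nominal level. The uncorrected sandwich variance is biased downwards, because it uses residuals from fitted means without allowing for the fitting. The normal reference also has shorter tails than the statistic it is applied to. Both make p-values too small and intervals too narrow.

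At stake are the reading of results just under 0.05 and the width of the intervals that describe the preliminary effects. The outcomes are mostly continuous, so methods that hold the level are available for the same data and visits.

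**Working it through.** **Inputs.** From the protocol: three arms, 20 per arm (3 × 20 = 60, which reproduces the stated total), three visits, two-sided 0.05, and COMBAT-ICU compared with each of the other arms. The 20 per arm comes from a cited method that is not at hand and is taken as given. Assumed, because the protocol is silent: complete data, no covariates, normal outcomes, separate means for each group and visit, and one contrast of change from baseline.

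**Uncorrected sandwich, normal reference.** In this setting the sandwich variance of a two-arm contrast is (n−1)/n times the unbiased variance. The Wald test therefore rejects when |t| on 2n−2 degrees of freedom exceeds 1.960 × √((n−1)/n).

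- n = 20: cut-off 1.960 × √(19/20) = 1.910; P(|t₃₈| > 1.910) = 0.0637.
- n = 16 (assumed completers): 1.960 × √(15/16) = 1.898; P(|t₃₀| > 1.898) = 0.0674.
- n = 14 (assumed completers): 1.960 × √(13/14) = 1.889; P(|t₂₆| > 1.889) = 0.0701.

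**Where the excess comes from, n = 20.** Unbiased variance with a normal reference: P(|t₃₈| > 1.960) = 0.0574. Sandwich variance with a t reference: 0.0558. Each part contributes roughly half.

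**Model-based variance pooled over three arms, normal reference.** With 3n−3 = 57 degrees of freedom, P(|t₅₇| > 1.960) = 0.0549.

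**Intervals and p-values, n = 20.** The sandwich multiplier is effectively 1.910. Against t₃₈ the ratio is 1.910/2.024 = 0.944 (5.6% too narrow); against t₅₇ it is 1.910/2.002 = 0.954 (4.6% too narrow). A t₃₈ p-value of 0.05 corresponds to a Wald statistic of 2.024/√0.95 = 2.077, that is p = 0.038. So on the 38-df comparison a reported p between 0.038 and 0.050 would lie above 0.05.

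**Checks by simulation under the null.** Two sets of 3,000 trials with fitted GEE (exchangeable correlation 0.5) gave 6.5% and 5.8%. The Monte Carlo standard error is about 0.4 points, so both agree with 6.4%. A direct simulation of the sandwich test with 20,000 trials gave 6.3%. With five baseline covariates at n = 20 it gave 6.4% for the change contrast and 7.3% for the end-of-intervention mean contrast.

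**Candidate remedies.** Type I error (%) of one contrast of change, 200,000 null trials, 20 per arm, complete data:

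| Scenario | Uncorrected sandwich, normal | Kauermann-Carroll sandwich, t | Arm-specific variance, Satterthwaite | Variance pooled over three arms, t |
|---|---|---|---|---|
| Equal SDs | 6.4 | 5.0 | 5.0 | 5.1 (exact 5.0) |
| COMBAT-ICU SD × 1.5 | 6.5 | 5.1 | 5.0 | 6.8 |
| COMBAT-ICU SD × 0.67 | 6.5 | 5.1 | 5.0 | 3.9 |
| Arm outside the contrast, SD × 1.5 | 6.4 | 5.0 | 5.0 | 2.1 |
| Arm outside the contrast, SD × 0.67 | 6.4 | 5.0 | 5.0 | 7.7 |
| Skewed integer score, 0–54 | 6.3 | 4.9 | 4.8 | 4.9 |

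Pooling over only the two compared arms is not safe either. With an assumed 20 versus 14 completers and an SD ratio of 0.67 or 1.5 it gave 3.7% to 6.8%, while the arm-specific version gave 4.9% to 5.0%.

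**The case against.** The strongest objection is that this is detail for a statistical analysis plan. The protocol gives the model family, comparisons, level, sidedness and software, which is normal depth. A plan that is not shown may settle the variance estimator, and nothing in the protocol rules out a corrected one. This stands in part, and it is why the figures are conditional. It does not remove the point: the protocol itself commits to this method at this level on this sample, and both ordinary large-sample forms checked miss the stated 0.05.

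A reader might infer that the protocol prescribes the uncorrected sandwich, so that 6.4% is the error rate of the planned analysis. The text does not support that. The choice is open, and under a pooled model-based variance the excess is only half a point. Nor is 6.4% exact for the analysis as planned, which may have dropout and covariate adjustment.

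A reader might also take a joint test of all group-by-visit terms as the planned test and expect a larger inflation. The protocol plans no such test, so no figure for one belongs here.

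A third objection is that a mixed model is a matter of preference and is not automatically better. This is right for a pooled covariance: the three-arm version ranged from 2.1% to 7.7% when one arm's SD differed, sometimes further from 5% than the uncorrected sandwich. GEE is a legitimate choice here, and keeping it with a corrected variance answers the concern.

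Finally, the excess is small in a pilot. That stands and sets the priority.

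**Conclusion.** The point holds in conditional form. Run with the uncorrected sandwich and a normal reference, the planned analysis would test a single contrast of change at about 6.4% rather than 5% (6.7% to 7.0% at an assumed 16 to 14 completers per arm). With a pooled model-based variance and a normal reference the figure is about 5.5%. These rest on complete data among those analysed, no covariates and, for the closed forms, normal outcomes; the pooled figure also needs equal arm variances.

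It would be too strong to conclude that the trial's findings would be invalid. The excess is 0.5 to 1.4 percentage points per contrast, the stated aim is preliminary effects and feasibility, and no decision rule depends on p < 0.05. This is a low-priority correction.

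**What to change.** State the small-sample provision before analysis, in Methods of Data Analysis or in the statistical analysis plan if there is one. For the PICSQ and the other continuous outcomes, choose one of two options:

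- Keep GEE, and specify a bias-corrected sandwich variance (for example Kauermann-Carroll) with a t reference for tests and intervals.
- Use a REML mixed model for repeated measures with group, visit and group-by-visit terms, unstructured within-person covariance that differs by arm, and Satterthwaite or Kenward-Roger degrees of freedom.

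Do not rely on one covariance pooled over the three arms. GEE may stay for binary and count outcomes such as mortality and readmission, which this check does not cover.

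The cost is a wording change with no new data or visits. Relative to the uncorrected sandwich, intervals become about 5% to 6% wider (2.002/1.910 = 1.048; 2.024/1.910 = 1.060). Arm-specific variance leaves at most 38 degrees of freedom for a two-arm contrast, against 57 when pooled. If SPSS 28.0 does not offer the chosen option, a second package must be named.

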and physical rehabilitation, with the latter receiving the most attention to date. A systematic review of 6 studies on exercise rehabilitation for ICU survivors who had been mechanically ventilated for at least 24 hours reported mixed findings on functional capacity, and no beneficial effect was documented on health-related QoL (HRQoL). Similar findings were reported by another meta-analysis of 10 studies that synthesized the evidence on physical rehabilitation among ICU survivors and found limited or no change in HRQoL or mortality. A full-scale randomized controlled trial (RCT) tested an 8-week home-based individualized and progressive multicomponent exercise program (N = 195) delivered through 3 home visits and 4 telephone calls. The other RCT (N = 150) tested a physiotherapist-led transitional rehabilitation program covering both the in-patient and out-patient period among patients admitted to ICU for at least 5 days. Compared to usual care with comprehensive in-patient exercise rehabilitation, the additional out-patient exercise training (multicomponent exercise for 8 weeks, 60 minutes/session, twice/week) did not show added benefits on physical function and HRQoL. The high lost to follow-up rate and incompleteness rate of out-patient exercise training might explain for its modest effects. The poor treatment compliance raises the concern that even cantered-based or gymnasium-based training can optimize the training with exercise equipment, the travelling demand for ICU survivors may serve as a significant barrier to hamper the adherence. Indeed, ICU survivors have cited travel to training centers and a lack of motivation as the major factors in their poor rehabilitation attendance.

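### GEE is the only effect analysis named, and its protection against severity-related dropout depends on a working correlation the protocol does not fix; a likelihood-based repeated-measures model would be safer at almost no cost

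*Protocol*

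**What the plan says.** Under Methods of Data Analysis the protocol states the principle, "The RCT data will be analyzed according to the intention-to-treat principle", and then the model: "Generalized estimating equation modelling will be performed to determine the effects of the COMBAT-ICU intervention". COMBAT-ICU is compared with the exercise and attention placebo groups over T0, T1 and T2. No other effect analysis is named. The section gives no working correlation, weighting or dropout assumption. Covariates enter only if they are on a short list of possible confounders and differ between groups at baseline with p ≤ 0.10. Baseline PICSQ is not on that list.

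Under Study intervention, COMBAT-ICU has 24 sessions of 80 minutes. The exercise arm has three 45-minute sessions a week for 8 weeks. The attention placebo arm has a call every 2 weeks for 8 weeks.

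On an earlier out-patient exercise trial, Study Background says: "The high lost to follow-up rate and incompleteness rate of out-patient exercise training might explain for its modest effects". No figure is given there, and no dropout rate is assumed anywhere for this trial.

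Under Sample Size: "we conservatively assume a small effect size (i.e. between 0.1 and <0.3) on the primary outcome (i.e. PICS"), and "The total sample size is therefore 60".

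**The concern.** Intention-to-treat says which participants and which arms are analysed. It does not say under what dropout assumption the estimate is valid. That comes from the model.

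Unweighted GEE is in general valid only when dropout is completely at random, given the covariates in the model. If dropout depends on earlier scores, GEE for a continuous outcome can still be nearly unbiased, because the working correlation lets the T0 values of those who leave inform the T1 mean. With an independence working correlation that link is cut. The T1 mean is then the mean of those still present, while the T0 mean is that of everyone randomised. If the more severely affected leave one arm more often, that arm appears to improve.

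Scheduled session time is 24 × 80 = 1,920 minutes in COMBAT-ICU and 24 × 45 = 1,080 minutes in exercise, against four calls in placebo. Dropout that differs by arm and is related to severity is therefore plausible. At stake are the preliminary effect estimates against placebo (objective 1) and the main trial that would be planned on them.

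**Working it through.** **The plan's own figure.** I read the assumed effect as being in SD units and take d = 0.2 as an assumed midpoint. With m per arm in the pilot, the main trial needs n = 2·[t]²/d² per arm, where t is the 80th percentile of a noncentral t with 2m − 2 degrees of freedom and noncentrality 1.96. At m = 20, n = 411, so pilot plus main trial for two arms is 2 × 411 + 2 × 20 = 862. That is the minimum, shared by m = 17 to 23. So 20 per group is consistent with minimising the combined size, and 3 × 20 = 60.

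**Inputs for the dropout check (assumptions, not in the protocol).** No true effect; unit-variance normal scores, higher = worse; T0–T1 correlation ρ = 0.6; everyone has T0; some lack T1. In the active arm the log odds of dropout are linear in T0, with odds ratio 1.65, 2.72 or 4.48 per SD. In placebo dropout is random.

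**Formula.** Let m₀ be the mean T0 score of those who stay in the active arm (the whole arm has mean 0). With separate means for each group and time and working correlation r, the T1 mean converges to the stayers' T1 mean plus r times the T0 shortfall:

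bias = ρ·m₀ + r·(0 − m₀) = (ρ − r)·m₀

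Independence is r = 0, giving 0.6·m₀. A correct working correlation is r = 0.6, giving 0.

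| Active-arm dropout | Odds ratio per SD | m₀ | r = 0 | r = 0.3 | r = 0.6 |
|---|---|---|---|---|---|
| 10% | 1.65 | −0.049 | −0.03 | −0.01 | 0 |
| 10% | 4.48 | −0.122 | −0.07 | −0.04 | 0 |
| 20% | 1.65 | −0.096 | −0.06 | −0.03 | 0 |
| 20% | 2.72 | −0.173 | −0.10 | −0.05 | 0 |
| 20% | 4.48 | −0.227 | −0.14 | −0.07 | 0 |
| 30% | 1.65 | −0.143 | −0.09 | −0.04 | 0 |
| 30% | 2.72 | −0.253 | −0.15 | −0.08 | 0 |
| 30% | 4.48 | −0.327 | −0.20 | −0.10 | 0 |

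Negative values favour the active arm. Simulation with 400,000 per arm agrees for independence: −0.055, −0.104 and −0.136 at 20%, and −0.085, −0.154 and −0.199 at 30%. A model conditioning on T0 was within 0.005 SD of zero.

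**Same severity mechanism in both arms, independence, odds ratio 2 to 3.** Dropout of 30% v 10% gives 0.07 to 0.10 SD, 20% v 5% gives 0.06 to 0.08, and 10% v 5% gives 0.02 to 0.03. Equal dropout gives zero.

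**Dropout driven by the unseen T1 score** (simulated; T0–T1 correlation 0.5; odds ratio 2 to 3). Even exchangeable or unstructured GEE is biased by 0.08 to 0.10 SD at 20% v 5% and by 0.12 to 0.17 SD at 30% v 5%.

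**Scale.** At 20 per arm with no losses, the standard error of an unadjusted T1 contrast is √(2/20) = 0.316 SD, and power at d = 0.2 is about 9%.

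**The case against.** The strongest reply is that this is detail for a statistical analysis plan. Working correlation, weighting and missing-data rules are often left there, that plan is not at hand, and the protocol nowhere says its GEE is unweighted. GEE for a repeated outcome is also a standard choice. All of this stands as far as silence goes: the missing detail is not itself an error. What remains is that the protocol has already chosen the estimator, and an alternative with a weaker dropout assumption runs on the same data and software.

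A reader might infer that GEE requires dropout unrelated to health, or that the planned analysis is biased by as much as the assumed effect. The documents do not support either. Baseline-driven dropout leaves almost no bias when the working correlation fits, and health-related dropout with the same rate and mechanism in both arms leaves none. The larger figures belong to an independence working correlation that the protocol has not chosen, and to dropout inputs it does not give.

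The cited loss to follow-up is weaker support than it looks. It arose in out-patient training, and Study Background points to travel as a barrier. This trial is home-based, and its weakest participants are trained by home visit. Leaving sessions is also not the same as missing an assessment. The unequal session load nevertheless remains.

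The argument applies mainly to the attention placebo comparison. Between COMBAT-ICU and exercise the dropout gap may be smaller, since both arms are demanding.

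**Conclusion.** The point holds in a limited form. The protocol ties its only effect analysis to a model whose robustness to severity-related dropout hinges on an unnamed working correlation, in a design where such dropout could well differ by arm. With T0–T1 correlation 0.6, 20–30% active-arm dropout, odds ratios of 1.65 to 4.48 per SD and random dropout in placebo, independence GEE would favour the active arm over placebo by 0.06 to 0.20 SD. The bias is about half that at a working correlation of 0.3, near zero at the correct value, and at most about 0.07 SD at 10% dropout.

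A reader might also infer that the pilot would declare a false effect. It rarely would: the bias is below the 0.32 SD standard error. But it runs in one direction, so it would shift the estimates carried into main-trial planning. This is a cheap improvement, not an error that invalidates the trial.

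**What to change.** In Methods of Data Analysis, for PICSQ and the other continuous outcomes, replace GEE with a linear mixed model for repeated measures, fitted by REML with unstructured covariance (SPSS MIXED). Use every observed T0, T1 and T2 value from all randomised participants, including values collected after the intervention was stopped. Report the number missing at T1 and T2 by arm, with reasons.

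If GEE is kept, specify an unstructured working correlation and rule out independence. Inverse-probability weighting is not advisable here: 20–30% loss from 20 per arm leaves only 20 × 0.2 = 4 to 20 × 0.3 = 6 dropouts per arm on which to fit the weights.

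The cost is a sentence or two, with no new data or software. The mixed model assumes approximately normal outcomes. Neither model corrects dropout driven by unobserved outcomes, so the by-arm reporting matters whichever is chosen.

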## **Subjects**

The COMBAT-ICU trial will be conducted in three hospitals in Hong Kong. The eligibility criteria are Chinese adults aged  $\geq 18$ , admitted to ICU for at least 4 days as patients often develop long-standing PICS when the length of ICU stay is more than 3 days, has been discharged home, able to perform basic activities of daily living before ICU admission, living with family, have an electronic device that can access the internet (patient/family) and able to walk for at least 10 meters (assisted or unassisted). Patients will be excluded if they cannot read Chinese, have musculoskeletal injury precluding exercise training, are receiving structured out-patient pulmonary or cardiac rehabilitation after discharge, or have clinically evident dementia or significant impairment from an acute brain problem (e.g. traumatic brain injury, stroke, subarachnoid hemorrhage or hypoxic brain injury) that precludes following the study protocol. Those with prolonged length of stay ( $\geq 28$  days) in the step-down wards will also be excluded as their long-term impairments are likely altered during the extended stay and treatments received in the post-ICU setting.

A research assistant will identify potential participants in the ICU, and then conduct eligibility screening and recruit participants on the day before their discharge from hospital and given one day for consideration after explanation of the informed consent. A study implementation protocol is shown in Appendix 1. After obtaining written consent, baseline data will be collected and participants will be randomised to the COMBAT-ICU, exercise or attention placebo groups. Block randomization will be performed and stratified on study sites, this stratification strategy can ensure balance group allocation of patients from different settings, where patients' socio-economic status and clinical practice may differ. Patients will be allocated in a 1:1:1 ratio according to a computer-generated random sequence list for each stratum. Sequentially numbered opaque sealed envelopes will be used to ensure allocation concealment.

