#### *Secondary outcomes*

**Performance-based physical function:** The 6-Minute Walk Test (6MWT) will be used to evaluate aerobic capacity and endurance. Standard measurement guidelines will be followed, and the distance walked will be recorded. The Time-Up-Go test will be used to measure functional mobility, assessed by the time it takes to stand up, walk a distance of 10 feet, turn, walk back and sit down. Handgrip strength will be assessed by a dynamometer to evaluate muscle strength of upper limbs. The Short Physical Performance Battery will be used to assess functional capacity. It consists of 3 timed tasks: standing balance, walking speed and chair stand tests.

**Performance-based cognitive function:** The Montreal Cognitive Assessment will be used to assess global cognition, and the Colour Trails Test to measure executive function and attention. The latter test has two parts: part 1 assesses visual-motor processing speed and attention, and part 2 sequencing and mental flexibility in addition to processing speed and attention. The Digit Span test will be used to measure short-term and working memory.

**Patient-reported mental health:** The Patient Health Questionnaire-9 will be used to measure the frequency of depressive symptoms in the past 14 days. Its 9 items are rated on a 4-point scale ranging from 0 to 3, with higher sum scores indicating more depressive symptoms. The Generalized Anxiety Disorder Scale-7 will be used to measure anxiety levels. Ratings on a 4-point scale (0-3) indicate the frequency of anxiety symptoms in the past 14 days, with higher total scores representing greater anxiety.

**HRQoL:** The EuroQol Five Dimensions Five Levels (EQ-5D-5L) will be used to measure HRQoL. It consists of two parts: EQ-5D descriptive system and EQ visual analogue scale. The first part uses 5 levels to indicate a participant's health state on 5 dimensions – mobility,

self-care, usual activities, pain/discomfort and anxiety/depression – and the second part is an additional self-rated health item rated on a visual analogue scale ranging from 0-100.

*Unplanned hospital readmission and mortality:* Hospital utilisation data and mortality will be monitored from T0 to T2 through electronic medical record review.

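### The covariate plan leaves out both the baseline value of the outcome and the stratifying hospital, so the GEE contrast reads as a change-score comparison: valid, but less precise than baseline adjustment

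*Protocol*

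**What the plan says.** All references are to the Protocol.

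- **Model.** Methods of Data Analysis plans a GEE "comparing the intervention group with the exercise and attention placebo groups across the study time-points". The model terms are not written out.
- **Covariates.** The same section treats five variables as "potentially confounding variables: age, sex, previous mental health problems, disease severity (APACHE II score), and negative ICU experience". The entry rule is a baseline p-value of 0.10 or less "for between-group differences at baseline will be statistically adjusted in the analysis".
- **Time-points.** Primary and Secondary Outcomes sets measurement "at baseline (T0), immediate post-intervention (T1) and 3 months post-intervention (T2"), so T0 is one of the three time-points.
- **Target of the future trial.** Sample Size describes the main trial's power as power "to detect between-group changes in the outcome at the post-intervention time points".
- **Randomisation.** Under Subjects, "Block randomization will be performed and stratified on study sites". The reason given is that patients' "socio-economic status and clinical practice may differ" between the three hospitals.
- **Outcomes without a T0 value.** "Hospital utilisation data and mortality will be monitored from T0 to T2", so readmission and mortality have no baseline measurement.

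**The concern.** The T0 value of an outcome is often its strongest single predictor at follow-up, and it is already collected here. Its worth as a covariate comes from that correlation, not from whether the arms happen to differ at baseline. The stated rule selects covariates by chance imbalance and does not name T0 at all. If T0 instead sits in the response with free means in each arm, the treatment contrast at T1 or T2 becomes a difference in mean change. That carries the full noise of the T0 measurement into the estimate.

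Hospital was judged important enough to stratify on, yet it is not an analysis variable. Stratified blocks make it nearly identical across arms, so a screen on baseline p-values would not bring it in.

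Preliminary effects are the first objective of the study. With 20 per arm, the estimates and their intervals are a main output for planning the next trial, so intervals wider than the data require are a real loss.

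**Working it through.** **Inputs from the Protocol.** 20 per arm, 60 in total (Sample Size); 1:1:1 allocation and three hospitals (Subjects); T0, T1 and T2 (Primary and Secondary Outcomes); two-sided 5% level (Methods of Data Analysis).

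**Assumptions.** The Protocol gives no T0-to-follow-up correlation ρ, so 0.3, 0.5 and 0.7 are shown. SDs are taken as equal at T0 and follow-up, and data as complete.

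**The plan's own figure.** Minimising the combined pilot and main-trial size for a two-arm comparison (80% power, two-sided 5%) at a standardised effect of 0.2, an assumed mid-point of the stated 0.1 to <0.3 band, gives a minimum total of 864. It is reached at 17 and equally at 20 per arm. So 20 per arm can be reproduced, 3 × 20 = 60 is exact, and n = 20 is used below.

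**Step 1: what the GEE contrast is.** A GEE with group, time and their interaction, with T0 in the response, was fitted to simulated complete data under independence and exchangeable working correlations. The T1 interaction equalled the difference in mean change from T0, with a largest discrepancy of 2 × 10⁻¹⁶.

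**Step 2: closed-form variance of a two-arm contrast, in SD units.**

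- Change score: 2(1 − ρ) × 2/n
- T0 as covariate: (1 − ρ²) × 2/n
- Follow-up value alone: 2/n
- Ratio of covariate-adjusted to change-score variance: (1 − ρ²) / [2(1 − ρ)] = (1 + ρ)/2, which is below 1 for every ρ < 1

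With n = 20, 2/n = 0.1:

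| ρ | SE, change score | SE, T0 as covariate | Reduction in SE | Equivalent n per arm, 20 ÷ [(1+ρ)/2] |
|---|---|---|---|---|
| 0.3 | √0.140 = 0.374 | √0.091 = 0.302 | 19% | 30.8 |
| 0.5 | √0.100 = 0.316 | √0.075 = 0.274 | 13% | 26.7 |
| 0.7 | √0.060 = 0.245 | √0.051 = 0.226 | 8% | 23.5 |

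Follow-up alone gives √0.1 = 0.316. Since 2(1 − ρ) > 1 when ρ < 0.5, the change score is then less precise than ignoring T0 altogether. At ρ = 0.5, with t on 38 degrees of freedom (2.024), the 95% half-width is 2.024 × 0.316 = 0.64 SD against 2.024 × 0.274 = 0.55 SD.

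**Step 3: simulation, linear models.** 3,000 three-arm trials of 20 per arm were run at each ρ, with an assumed shift of 0.5 SD between adjacent hospitals. Empirical SDs of the T1 contrast at ρ = 0.3 / 0.5 / 0.7 were:

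- change score: 0.378 / 0.313 / 0.248
- T0 adjusted: 0.308 / 0.273 / 0.230
- T0 and hospital: 0.307 / 0.273 / 0.230

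Mean contrasts under the null were near zero for the change-score and T0-adjusted analyses.

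**Step 4: simulation, GEE with uncorrected robust SE.** There were 60 participants in hospitals of 21/21/18, stratified 1:1:1, with exchangeable correlation and 5,000 runs per setting. The hospital SD was constant over time at 0, 0.3 or 0.5 (all assumed). At hospital SD 0.3 the empirical SEs of the T1 contrast were:

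- T0 as response: 0.374 / 0.321 / 0.245, the same to three decimals with or without hospital in the model
- T1 and T2 as response, T0 and hospital as covariates: 0.304 / 0.279 / 0.228

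Mean type I error over the nine settings was 6.5% and 7.1% respectively.

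**The case against.** **No model equation is given.** Whether T0 is a free response, a constrained response or a covariate is often left to a statistical analysis plan, which may exist. The wording would also fit T0 as a response with means constrained equal. The Sample Size phrase describes the future main trial, so it is only secondary support for the change-score reading. This stands as a caution about the reading. It does not remove the point, because the Protocol itself fixes a covariate list and an entry rule, and those plan for neither T0 nor hospital.

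**The rule may cover any baseline variable.** On that wider reading an imbalanced T0 could enter. It would still enter only after chance imbalance, and under the natural reading it would then be response and covariate in the same model.

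**The planned contrast is valid.** It is: no bias was seen, and the loss is one of precision. Its size depends on an unknown correlation; at 0.8 the reduction in SE is only 5%. The direction holds for every correlation below 1.

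**Hospital makes no difference.** This largely stands. An effect constant over time cancels from a change score, and after T0 adjustment hospital altered the SD by under 1%. Hospital effects that vary over time were not examined.

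**The change is not free.** With an uncorrected robust SE, type I error rises slightly, and it is above 5% either way. The empirical SEs in the working measure actual spread, so the gain is not produced by understated robust errors.

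**Dropout.** All figures assume complete data. If T1 and T2 are the only responses, a participant with T0 alone contributes nothing, which bears on the intention-to-treat statement. The constrained-baseline form keeps that participant in the analysis.

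**Conclusion.** The point holds. The stated covariate rule plans for neither the T0 outcome nor the stratification factor, and on the natural reading the main contrast is a change-score comparison. For outcomes measured at T0, including the primary PICS questionnaire, the standard error is larger than it need be. Adjusting for T0 would lower it by 19%, 13% or 8% at correlations of 0.3, 0.5 or 0.7.

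These sizes assume equal SDs, complete data and a saturated group-by-time model. The hospital part is a design-analysis inconsistency with almost no effect on the contrast when hospital effects are constant over time. The planned estimate is not invalid. This is a change that should be made because it is cheap and improves a main output of the pilot.

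**What to change.** In Methods of Data Analysis, for every outcome measured at T0, state one of the following:

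1. T1 and T2 are the responses, with the T0 value of that outcome and hospital (three-level fixed effect) as prespecified covariates, regardless of baseline p-values; or
2. T0, T1 and T2 are the responses, with T0 means constrained equal across arms and hospital included. The working correlation must not be independence here. Under independence the T0 data would not inform the T1 and T2 contrasts, which would reduce to comparisons of follow-up values alone.

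For unplanned readmission and mortality, which have no T0 value, include hospital only where the number of events allows.

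The cost is one or two sentences and no new data. The first form uses three degrees of freedom (one for T0, two for hospital). With an uncorrected robust SE, simulated type I error rises from about 6.5% to 7.1%. Both figures exceed 5%, so the small-sample behaviour of the robust SE deserves attention whichever model is chosen.
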